**ODS OUTUT ParameterEstimates=pest;**

Estimates from PROC GENMOD along with patients’ data will be used to calculate the probability, the p used for Bernoulli distribution, for each patient.

Observed data will be duplicated 100 times creating 100 sets of data. In each dataset, the SAS function **RAND(“Bernoulli”, p)** will be used to determine LoAC status (1=having LoAC, 0=not having LoAC) for patients with missing data due to reasons other than lack of efficacy or due to asthma-related AEs.

**Step 2:** Analysis

The 100 sets of data will be analyzed in a manner analogous to the analysis as described in Section 6.2.2 adding a by-statement for imputation to the SAS procedure.

The results from the 100 analyses will be combined using Rubin’s formulae in the following SAS procedure.

**PROC MIANALYZE DATA=diff;**

**MODELEFFECTS** estimate;

**STDERR** stderr;

**RUN;**

### 6.3. Key Secondary Efficacy Endpoints and Analyses

The key secondary efficacy endpoints are listed in Section 1.2. Analyses will be based on the ITT analysis set.

#### 6.3.1. Time from Randomization to LoAC During Treatment Period

The time (days) from randomization to LoAC during the treatment period is the interval from the randomization to the occurrence of the LoAC.

The observation for each patient is the interval from randomization to the occurrence of the LoAC, or censoring, whichever occurs earlier and an indicator whether or not the observation is for a LoAC case or censoring.

The observations are derived as:

1. Time to event or censoring: the date of censoring or the date of LoAC, whichever occurs earlier - the date of randomization + 1.
2. Indicator variable: 1 if a LoAC case is observed; 0 otherwise.

Patients who withdraw from the study before the week 16 or discontinue treatment due to lack of efficacy, LoAC, or an asthma-related adverse event will be analyzed as having experienced LoAC at the time of the withdrawal or treatment discontinuation.

Patients who withdraw from the study before week 16 without LoAC or early withdraw from treatment without LoAC during the treatment period (section 1.7) for other reasons will be analyzed as being right-censored at the time of withdrawal.

Patients who completed treatment without experiencing LoAC will be right-censored at the time of treatment completion.

The Kaplan-Meier (KM) method will be used to estimate and compare the distributions of time to LoAC between treatment groups. A one-sided log-rank test will be provided to compare the hazard ratio (TEV-48574/placebo) between the TEV-48574 and placebo groups.

Example SAS code for hazard ratio

**ODS OUTPUT PARAMETERESTIMATES=***name*;

**PROC PHREG DATA=** *NAME*;

**MODEL AVALN\*CENSOR(1)=** TRTPN/**RISKLIMITS**;

**RUN;**

Notes, for the hazard ratio of active/placebo, the TRTPN should have a value 2 for active and 1 for placebo.

Example SAS code for log-rank test

**ODS OUTPUT HOMTESTS=***name* (**WHERE=(UPCASE(TEST) = "LOG-RANK")**);

```

PROC LIFETEST DATA=name;
  TIME AVALN*CENSOR(1);
  STRATA TRTP;
RUN;

```

Example SAS code for KM estimates

```

ODS OUTPUT PRODUCTLIMITESTIMATES=name QUARTILES=name
CENSOREDSUMMARY = name;

```

```

PROC LIFETEST DATA=name OUTSURV=name TIMELIST=x TO y BY n ;
  TIME AVALN*CENSOR(1);
  BY TRTP;
RUN;

```

Where AVALN denotes the time-to-event (days); CENSOR denotes censoring (1= censoring and 0=event); TRTP/TRTN denote the planned treatment group.

### 6.3.2. Asthma Control Questionnaire 6-Question Version (ACQ-6) at End of Treatment (EOT) and Throughout Study

The ACQ-6 is a validated asthma assessment tool that has been widely used. Six questions are self-assessments (completed by the patient). Each item on the ACQ-6 has a possible score ranging from 0 to 6, and the total score is the mean of all responses (See Appendix E of the study protocol). ACQ-6 will be administered at the sites at screening, run-in, all on-site visits during treatment period (visits 1, 2, 3, 4, 6, 7, 8, 9, and 10), and follow-up visit (visit 11).

The analysis will be based on ITT and PP analysis sets.

The changes from baseline in ACQ-6 total score at EOT will be analyzed using an analysis of covariance (ANCOVA) method. The model will include treatment as the fixed effect and baseline weight, age group (<65 years vs ≥65 years), gender, and baseline value of ACQ-6 total score as covariates. LS mean and SE for each treatment group, LS means and corresponding 95% confidence intervals for the treatment differences (TEV-48574 - placebo), and the associated p-values from the overall results for treatment comparisons.

For patients who did not complete the treatment period, data from the early termination (ET) visit will be used for the analysis. For patients who are lost-to-follow-up (no ET assessment) prior completion of the treatment period, the last assessment during the treatment period will be used for the analysis.

Example SAS code for ANCOVA

```

PROC MIXED DATA=<name>;
  CLASS TRTP AGEGR1 SEX;
  MODEL CHG= BASE TRTP WEIGHT AGEGR1 SEX /S;
  LSMEANS TRTP /DIFF=CONTROL (“Placebo”) CL ALPHA=0.05;
  ODS OUTPUT LSMEANS= <name> DIFFS= < name> ;
RUN;

```

Where TRTP denotes the planned treatment group; CHG denotes the change from baseline at EOT; BASE denotes the baseline ACQ-6 total score;

The changes from baseline in ACQ-6 total score **throughout the study** will be analyzed using the mixed model for repeated measures (MMRM) with treatment group, visit, treatment and visit interaction, and baseline value of ACQ-6 total score as fixed effects and patient as a random effect. The unstructured covariance structure (UN) will be used to model intra-subject correlation. LS mean and SE for each treatment group, LS means and corresponding 95% confidence intervals for the treatment differences (TEV-48574 - placebo), and the associated p-values from the overall results for treatment comparisons.

Notes, if UN dose not converge, compound symmetry (CS) will be used.

Data from visits 2 to 10 except visit 5 (phone contact, no data will be collected) will be included in the analysis model.

Per the ICE handling strategy, for patients who did not complete the treatment period, observations after the end of the treatment period will be discarded and treated as missing observations.

The overall and by-visit results will be presented. The endpoint will be measured by the overall results. Descriptive statistics from each visit will be provided.

Example SAS codes for MMRM analysis:

```
PROC MIXED DATA=<name> METHOD=REML;
  CLASS USUBJID TRTP AVISIT AGEGR1 SEX;
  MODEL CHG=BASE TRTP WEIGHT AGEGR1 SEX AVISIT TRTP*AVISIT/S;
  REPEATED AVISIT/ SUB=USUBJID TYPE=UN;
  LSMEANS TRTP TRTP*AVISIT/ DIFF CL DDFM=KR ALPHA=0.05;
  ODS OUTPUT LSMEANS= <name> DIFFS= <name> ;
RUN;
```

Where TRTP denotes the planned treatment group; AVISIT denotes the visits; BASE denotes the baseline ACQ-6 total score; CHG denotes the change from baseline at each visit.

### 6.3.3. Forced Expiratory Volume in First Second (FEV1) (% Predicted, L) at EOT and Throughout Study

Spirometry will be performed both at the site and by hand-held spirometer. On-site spirometry will include full-flow volume loops (FVC, FEV1, FEV1/FVC, FEF25%-75% and PEF) and reversibility testing at all visits during treatment period except the phone visit. Hand-held spirometry (FEV1, PEF) will be performed daily.

Analyses will be based on-site FEV1.

The change from baseline in FEV1 **at EOT** will be analysis using ANCOVA in a manner analogous to the analysis as described in Section 6.3.2 using the same algorithm for patients who did not complete the treatment period or patients who are lost-to-follow-up (no ET assessment) prior completion of the treatment period.

The changes from baseline in FEV1 **throughout study** will be analyzed using analyzed using MMRM in a manner analogous to the analysis as described in Section 6.3.2. Per the ICE handling strategy, for patients who did not complete the treatment period, observations after the end of the treatment period will be discarded and treated as missing observations.

The baseline FEV1 will be used in the analysis models.

#### 6.3.4. Use of SABA Quick Relief Medication at EOT and Throughout Study

The number of inhalations/puffs of SABA/quick-relief inhaler will be recorded in the e-diary daily. Study sites will monitor rescue medication use during the study visits screening and run-in visit, all visits during treatment period, and follow-up visit. Study sites are also responsible for responding to asthma specific alert criteria related to SABA/quick-relief inhaler use.

Analysis windows throughout the study for during the treatment period and post-treatment (follow-up period) will be derived for each patient using algorithm detailed in Section 6.1.1.

The daily average of the inhalations/puffs of SABA/quick-relief inhaler in each monthly analysis window will be calculated using formula below:

$$\frac{\sum \text{inhalations/puffs in an analysis window}}{\text{number of days in an analysis window}}$$

The baseline daily average of use of SABAs will be calculated based on the data from 7 days preceding day of randomization similarly.

The change from baseline in the daily average of the uses of SABA quick relief medication at EOT will be analysis using ANCOCA in a manner analogous to the analysis as described in Section 6.3.2. For patients who did not complete the treatment period, the last analysis window during the treatment period will be used. For patients who are lost-to-follow-up (no ET assessment) prior completion of the treatment period, the last analysis window during the treatment period will be used for the analysis.

The change from baseline in the daily average of the use of SABA quick relief medication throughout study will be analyzed using MMRM in a manner analogous to the analysis as described in Section 6.3.2. Per the ICE handling strategy, for patients who did not complete the treatment period, observations after the end of the treatment period will be discarded and treated as missing observations.

The baseline daily average of use of SABAs will be included in the analysis models.

In additional, weekly analysis windows (weeks 1 to 8) will be derived for each patient using algorithm detailed in Section 6.1.1. The daily average of the inhalations/puffs of SABA/quick-relief inhaler in each weekly analysis window will be calculated similarly using formula above. The change from baseline in the daily average of the use of SABA quick relief medication during weeks 1 to 8 will be analyzed using MMRM similarly.

#### 6.4. Other Secondary Efficacy Endpoints and Analyses

The other secondary efficacy endpoints are listed in Section 1.2. Analyses will be based on the ITT analysis set.

#### **6.4.1. Proportion of Patients Who Have a CAE During Treatment Period**

A clinical asthma exacerbation (CAE) during the treatment period CAE is defined as a worsening of asthma symptoms resulting in any of the following:

- The use of systemic corticosteroids (oral or injectable)
- An emergency department visit due to asthma treated with systemic corticosteroids
- An inpatient hospitalization due to asthma.

Worsening asthma includes new or increased symptoms or signs that either worry the patient, or are related to an asthma-specific alert (if available through the e-diary/hand-held spirometer).

A patient who meets criteria for a CAE will be treated per the local standard of care. Additional medication and/or medical intervention that would satisfy the definition of CAE occurring within 7 days of the last day of a prior CAE event will be considered as part of the same event for analysis purposes.

CAEs will be assessed at visits (screening and run-in, visits during treatment period, follow-up).

Proportion of patients who have a CAE during the treatment period will be analyzed in a manner analogous to the analysis for LoAC as described in Section 6.2.2. Similar approach for handling ICEs will be applied.

#### **6.4.2. Time from Randomization to First CAE During Treatment Period**

CAEs are a subset of LoAC events. Asthma exacerbation is defined as a worsening of asthma symptoms (examples are described below) resulting in any of the following:

- The use of systemic corticosteroids (oral or injectable)
- An emergency department visit due to asthma treated with systemic corticosteroids
- An inpatient hospitalization due to asthma.

CAEs will be assessed at screening and run-in visit, all visits during treatment period, and follow-up visit.

Time from randomization to first CAE during the treatment period will be analyzed in a manner analogous to the analysis of the time to LoAC as described in Section 6.3.1. Patients who early terminated from the study or treatment due to lack of efficacy or asthma-related AEs will be also treated as CAE. Patients who withdraw from the study before week 16 without LoAC or early withdraw from treatment without LoAC during the treatment period for other reasons will be analyzed as being right-censored at the time of withdrawal. Patients without CAE will be right-censored at the time of treatment completion.

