## 6.2. Primary Efficacy Endpoint and Analysis

### 6.2.1. Definition

The primary efficacy endpoint is the proportion of patients who experience loss of asthma control (LoAC) during the treatment period.

LoAC is defined as any one of the following during the treatment period:

- Morning PEF decrease  $\geq 30\%$  from baseline on 2 consecutive days or morning handheld FEV1 decrease  $\geq 20\%$  from baseline on 2 consecutive days
- Increase in SABA/quick-relief medication  $\geq 6$  puffs over baseline use in 24 hours on 2 consecutive days
- Increase in ICS dose  $\geq 4x$  most recent dose
- Systemic corticosteroid use
- Asthma ER visit or hospitalization

LoAC will be determined and recorded by investigator from study sites. A patient who meets criteria for LoAC will discontinue IMP, and resume or increase background asthma controller therapies, but will remain in the study. LoAC events will be treated by the investigator according to local standard of care.

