### 6.2.2. Primary Efficacy Analysis

The primary analysis will compare rates of LoAC between treatment groups using logistic regression with fixed effect for treatment, age group (<65 years vs  $\geq 65$  years) and gender, as well as baseline FEV1 and baseline weight as covariates. Patients who withdraw from the study before the week 16 or early terminated the study treatment due to lack of efficacy, LoAC, or an asthma-related adverse event will be analyzed as having experienced LoAC. Patients who withdraw from the study before the week 16 without LoAC or early terminated from the study treatment without experiencing LoAC during the patient's treatment period (Section 1.7) for other reasons will be analyzed as not experiencing LoAC. Asthma-related adverse events will be determined by blinded data reviews prior to the final database lock.

The treatment effect will be tested at a one-sided alpha of 0.1.

The primary analysis will be performed on the ITT analysis set. The rates of LoAC for each treatment group, confidence intervals, and p-value will be displayed.

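### The CAE analyses count some treatment stops as exacerbations without any CAE criterion, and SAP 6.4.1 and 6.4.2 can treat IMP stops for LoAC differently

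*SAP*

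**What the plan says.** SAP 6.4.1 and 6.4.2 define a CAE as worsening asthma that leads to systemic corticosteroids, an emergency department visit treated with them, or inpatient hospitalization. SAP 6.4.2 also notes that "CAEs are a subset of LoAC events".

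The handling of treatment stops is spread over several sections:

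- SAP 6.4.1 (proportion with CAE) gives no list of reasons. It refers to the LoAC analysis in 6.2.2 and says "Similar approach for handling ICEs will be applied".
- SAP 6.2.2 covers patients who withdraw or who "early terminated the study treatment due to lack of efficacy, LoAC, or an asthma-related adverse event will be analyzed as having experienced LoAC".
- SAP 6.4.2 (time to first CAE) is analysed like 6.3.1 but has its own sentence: "Patients who early terminated from the study or treatment due to lack of efficacy or asthma-related AEs will be also treated as CAE". It then censors at withdrawal those who leave for other reasons without LoAC, and adds "Patients without CAE will be right-censored at the time of treatment completion".
- SAP 6.3.1, the model for 6.4.2, covers patients who withdraw or "discontinue treatment due to lack of efficacy, LoAC, or an asthma-related adverse event will be analyzed as having experienced LoAC at the time" of that withdrawal or discontinuation.
- SAP 6.2.1 makes stopping IMP a consequence of LoAC: "A patient who meets criteria for LoAC will discontinue IMP, and resume or increase background asthma controller therapies, but will remain in the study".

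**The concern.** LoAC is a broad composite that can be met by two days of low PEF or FEV1, or by extra SABA puffs. CAE is the narrower, clinically treated part of it. The CAE endpoints are useful because they show whether an effect on LoAC extends to treated exacerbations.

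Two features of the SAP weaken that. First, a stop for lack of efficacy or an asthma-related AE is scored as a CAE with no CAE criterion met. This is stated outright in 6.4.2. Second, a patient who stops IMP for a LoAC that is not a CAE has no clear place. The rule borrowed by 6.4.1 names LoAC as a reason, while the rule written in 6.4.2 does not. Two programmers could score the same patient differently, and the two CAE analyses could rest on different sets of events. To the extent that LoAC stops are counted as CAEs, agreement between the LoAC and CAE results would be partly built in by the rule.

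**Working it through.** **The plan's own figure.** The only event rates given are for LoAC: 27% on placebo and 10.8% on TEV-48574 (Protocol 9.1, SAP 2.4). With pooled rate 0.189, one-sided alpha 0.1 and 80% power, the chi-square formula gives

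n = [1.2816 × √(2 × 0.189 × 0.811) + 0.8416 × √(0.27 × 0.73 + 0.108 × 0.892)]² / (0.27 − 0.108)² = (0.7096 + 0.4559)² / 0.02624 ≈ 51.8, so 52 evaluable per arm.

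52 / 0.85 = 61.2, so 62 randomized per arm, as stated. No corresponding figure exists for CAE.

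**Reasons that turn a stop into an event, side by side.**

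- SAP 1.7 (primary estimand): lack of efficacy, asthma-related AE, for patients without LoAC.
- SAP 6.2.2 and 6.3.1 (LoAC): lack of efficacy, LoAC, asthma-related AE.
- SAP 6.4.1 (CAE proportion): none listed; borrowed.
- SAP 6.4.2 (time to CAE): lack of efficacy, asthma-related AE.

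**One hypothetical patient.** FEV1 falls enough for LoAC in week 7. No corticosteroids, emergency visit or admission follow. IMP stops; the last dose was at week 6.

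- 6.4.1, taking 6.2.2 literally: stopped treatment for LoAC, so scored as CAE.
- 6.4.1, taking the strategy in 1.7: LoAC is not an imputation reason, so not a CAE.
- 6.4.2, by its own sentence: not a CAE. The censoring-at-withdrawal sentence does not fit, because it covers only patients without LoAC. The last sentence censors at treatment completion, which this patient never reaches.
- 6.4.2, by analogy with 6.3.1: LoAC is a listed reason, so scored as CAE at discontinuation.

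The censoring date is also open. SAP 1.7 ends this patient's treatment period at last dose + 14 days, that is 6 + 2 = week 8. Follow-up to EOT would run to week 16, a difference of 8 weeks.

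**Is the imputation needed?** Patients with LoAC stay in the study, and the LoAC and CAE inquiry continues at every visit through EOT and EOS (Protocol Tables 3 and 4). For patients who stop IMP only, CAE status is therefore normally observed.

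**Size of the LoAC route (illustration).** Let s be the share of LoAC patients with a true CAE, and q the share of the remaining LoAC patients scored as CAE. Neither is in the documents.

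Scored CAE rate = LoAC rate × [s + q(1 − s)]

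- q = 0 (only true CAEs counted): for s = 25%, 50%, 75%, placebo 6.8%, 13.5%, 20.3%; TEV-48574 2.7%, 5.4%, 8.1%.
- q = 1 (every LoAC stop scored): 27% and 10.8% for any s. The ratio to the true rate runs from 27/6.75 = 4 to 27/20.25 = 1.3.
- Scored CAEs as a share of LoAC, for s from 25% to 75%: 44% to 81% at q = 0.25, and 93% to 98% at q = 0.9.

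The number of stops for lack of efficacy or an asthma-related AE cannot be sized either, since the 15% dropout allowance is not split by reason.

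**The case against.** The strongest reply is that 6.4.2 restates the rule for CAE and leaves LoAC out, and that its final censoring sentence can be read to cover a patient with LoAC but no CAE. SAP 1.7, where the strategy for intercurrent events is set out, limits imputation to lack of efficacy and asthma-related AEs in patients without LoAC. On that view, the word LoAC in 6.2.2 only says that patients who stopped for LoAC had LoAC, and a proper CAE analogue would replace LoAC with CAE throughout. The protocol points the same way: section 4.4.1 separates LoAC stops from other IMP discontinuations, and section 7.1.1 keeps LoAC out of the adverse events unless it is more severe than the patient's usual course.

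This stands as an argument about intent. It defeats any claim that LoAC stops enter the CAE count automatically as lack of efficacy or asthma-related AEs. It does not settle 6.4.1, which refers to 6.2.2 and lists no reasons of its own, and the SAP prevails where it differs from the protocol. It also leaves the explicit sentence in 6.4.2 untouched.

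A second reply is that counting lack-of-efficacy and asthma-AE stops is a legitimate composite that matches the primary analysis. That is fair as a choice of estimand, but the result should not then be reported as the proportion with, or time to, a CAE as defined. It is also fair that observation up to week 16 includes time after IMP has stopped and controllers have been resumed or increased, which SAP 1.7 warns about.

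**Conclusion.** The point holds in two parts. SAP 6.4.2 scores stops for lack of efficacy or an asthma-related AE as CAEs although no listed criterion need be met. And 6.4.1 and 6.4.2 do not give one clear answer for a patient who stops IMP for a non-CAE LoAC; read literally, that patient could be a CAE in one analysis and not in the other.

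A reader might infer that the CAE endpoints become nearly the same as LoAC, or are overstated by a fixed factor such as three. The documents do not support either. Equality at 27% and 10.8% needs every LoAC stop to be scored as CAE, and even the literal rule may miss a LoAC after the week 14 dose, when no IMP remains to be stopped. The inflation of 1.3-fold to 4-fold is an upper illustration resting on an assumed CAE share of 25% to 75%; if LoAC stops are not scored, there is none from this route.

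CAE is an other secondary, hypothesis-generating endpoint (SAP 1.2 and 7). Primary power and type I error are unaffected. The wording should still be corrected, because it decides what is counted as an exacerbation.

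**What to change.** In SAP 6.4.1 and 6.4.2:

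1. Count a CAE only when one of the three listed criteria is recorded.
2. State that an IMP stop for LoAC without such a criterion is not a CAE.
3. Use the same end of observation for these patients in both sections, which is also the censoring date in 6.4.2. Say whether it is last dose + 14 days (SAP 1.7) or week 16, or study withdrawal if earlier. SAP 1.7 must be reconciled with the inclusion of post-discontinuation data in the ITT set (SAP 3.1).
4. If a composite that adds stops for lack of efficacy or an asthma-related AE is wanted, name it as a composite and report it as supplementary.

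The cost is mainly SAP wording, since LoAC and CAE are already captured on their own CRF pages (Protocol 7.1.1); item 3 also requires a decision on the estimand. Events will be fewer and precision lower. With 62 per arm and an assumed 50% share, about 8.4 and 3.3 true CAEs would be expected on placebo and TEV-48574 (62 × 13.5% and 62 × 5.4%), against 16.7 and 6.7 if every LoAC stop were scored.
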